#### **Appendix 4: Creatinine-based 2009 Revised Bedside Schwartz Equation**

eGFR = 0.413 x (height/Scr) if height is expressed in centimeters

##### Abbreviations / Units

eGFR (estimated glomerular filtration rate) = mL/min/1.73 m^2

Scr (standardized serum creatinine) = mg/dL

## Appendix 5: Contraceptive Guidance

### Definitions

**Women of Childbearing Potential:** premenopausal females who are anatomically and physiologically capable of becoming pregnant following menarche.

**Women of Nonchildbearing Potential:**

1. **Surgically sterile:** females who are permanently sterile via hysterectomy, bilateral salpingectomy, bilateral tubal occlusion, and/or bilateral oophorectomy by reported medical history and/or medical records. Surgical sterilization to have occurred a minimum of 3 months prior to screening.

**Fertile male:** a male that is considered fertile after puberty.

**Infertile male:** permanently sterile male via bilateral orchiectomy.

### Contraception Guidance

#### Female Patients

Female patients who are of nonchildbearing potential will not be required to use contraception. Female patients of childbearing potential must be willing to use 2 methods (1 primary and 1 secondary method) of birth control from the time of signing the ICF until 9 weeks after the last dose of investigational medicinal product (IMP). Primary (non-barrier) methods of contraception include:

- hormonal injection (as prescribed)
- combined oral contraceptive pill or progestin/progestogen-only pill (as prescribed)
- combined hormonal patch (as prescribed)
- combined hormonal vaginal ring (as prescribed)
- hormonal implant
- hormonal or non-hormonal intrauterine device
- vasectomized male partner (sterilization performed at least 90 days prior to the Screening Visit, with verbal confirmation of surgical success, and the sole partner for the female patient).

Secondary (barrier) methods of contraception include:

- male condom with spermicide
- female condom with spermicide
- over-the-counter sponge with spermicide
- cervical cap with spermicide (as prescribed)
- diaphragm with spermicide (as prescribed).

Female patients of childbearing potential should refrain from donation of ova from screening until 9 weeks after the last dose of IMP.

## Male Patients

Male patients will be surgically sterile for at least 90 days, with documented azoospermia, or when sexually active with female partners of childbearing potential will be required to use a male condom with spermicide from screening until 17 weeks after the last dose of IMP. Sexual intercourse with female partners who are pregnant or breastfeeding should be avoided unless condoms are used from the time of the first dose until 17 weeks after the last dose of IMP. Male patients are required to refrain from donation of sperm from screening until 17 weeks after the last dose of IMP.

## Sexual Abstinence and Same-sex Relationships

Patients who practice true abstinence, because of the patient's lifestyle choice (i.e., the patient should not become abstinent just for the purpose of trial participation), are exempt from contraceptive requirements. Periodic abstinence (e.g., calendar, ovulation, symptothermal, postovulation methods) and withdrawal are not acceptable methods of contraception. If a patient who is abstinent at the time of signing the ICF becomes sexually active they must agree to use contraception as described previously.

For patients who are exclusively in same-sex relationships, contraceptive requirements do not apply. If a patient who is in a same-sex relationship at the time of signing the ICF becomes engaged in a heterosexual relationship, they must agree to use contraception as described previously.

## Appendix 6: Assessment in Pediatric Neuro-oncology (RAPNO) Criteria

Response definitions: patients must meet **ALL** criteria in each response/stable disease category, or **ANY** criteria in the progressive disease category

	Complete Response (CR)	Partial Response (PR)	Stable Disease	Progressive Disease (PD)
Criteria	Must meet ALL criteria	Must meet ALL criteria	Must meet ALL criteria	Must meet ANY criteria
MRI-brain	Complete disappearance of all disease (enhancing and non-enhancing, measurable and nonmeasurable) for a minimum of 4 weeks; no new lesions	≥50% decrease (compared with baseline) in the sum of the products of perpendicular diameters of all (up to 4) measurable lesions sustained for at least 4 weeks; no progression of nonmeasurable disease	Does not meet criteria for CR, PR, or PD	≥25% increase (compared with smallest measurement at any timepoint) in the sum of the products of perpendicular diameters of all measurable lesions; significant progression of nonmeasurable disease not attributed to prior therapy; any new tumor (any new lesions suspected to be treatment related should be confirmed by biopsy)
MRI-spine	Complete disappearance of all disease (enhancing and non-enhancing, measurable and nonmeasurable) for a minimum of 4 weeks; no new lesions	≥50% decrease (compared with baseline) in the sum of the products of perpendicular diameters of all measurable lesions sustained for at least 4 weeks; no progression of nonmeasurable disease. If negative at baseline, must remain negative	Does not meet criteria for CR, PR, or PD	≥25% increase (compared with smallest tumor measurement at any timepoint) in the sum of the products of perpendicular diameters of all (up to 4) measurable lesions; significant progression of nonmeasurable disease not attributed to prior therapy; any new tumor (any new lesions suspected to be treatment related should be confirmed by biopsy)
CSF cytology	If tumor cells are present at baseline, must be negative × 2 (sampling at least 2 weeks apart)	If absent (negative) at baseline, must remain absent. If present at baseline, can be present or absent	If absent at baseline, must remain absent. If present at baseline, can be present or absent	Previously absent tumor cells in CSF now present (positive)
Neurologic exam a	Stable or improving	Stable or improving	Stable or improving	Clinical deterioration not attributable to other causes
Steroid use	Off steroids or physiologic replacement doses only	Stable or less than baseline dose	Stable or less than baseline dose	
Extra-CNS disease	If positive at any timepoint, must be re-evaluated and have no evidence of disease	No new sites of disease	No new sites of disease	New sites of disease
Serum or CSF AFP, βhCG (if obtained, eg, germ cell tumors)	Must be within normal range for age			A previously negative (normal) assessment becomes positive

Abbreviations: βhCG=beta human chorionic gonadotropin; AFP=alpha-fetoprotein; CNS=central nervous system; CSF=cerebrospinal fluid; MRI=magnetic resonance imaging.

a If it is unclear that the patient has disease progression, it may be a reasonable option to keep the patient on study until subsequent assessments (e.g., MRI, CSF cytology) confirm progression. If subsequent testing confirms progression, the date of progression should be backdated to the onset of neurologic deterioration.

Adapted from Warren et al. 2018. Available at: <https://www.ncbi.nlm.nih.gov/pmc/articles/PMC5761545/>

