### 7.3.2. Response Evaluation, Overall Response Rate, and Duration of Response

Response, as defined by the RAPNO criteria (Warren et al. 2018; see Appendix 6) will be assessed in Part 1 at the EOT Visit. In Part 2, response will be assessed at end of Cycle 1 and Cycle 3, EOT Visit, then 26, 39, and 52 weeks post first dose, followed by 78 and 104 weeks post first dose of Lu-DTPA-omburtamab. Notably, objective response and stable disease requires that all criteria are met, while progression is defined when any of the PD criteria are met.

The ORR will be calculated from baseline MRI scans and from scans after the dosing of Lu-DTPA-omburtamab using 2 methods: firstly, by considering MRI data, neurological examination, and CSF cytology data together (RAPNO criteria); secondly, by considering CSF cytology data only. ORR will be defined as the proportion of all evaluable patients achieving a CR or PR as best overall response at the time of assessment.

Investigator-assessed DoR (Part 2) is defined as the time from response (CR or PR) to progression. Patients without any sign of progression will be censored at the date of their last PFS assessment.

In Part 1 and Part 2, the baseline CSF cytology assessment must be completed within 3 weeks prior to the first Lu-DTPA-omburtamab treatment dose infusion. Cerebrospinal fluid cytology should be assessed as positive/negative. Cerebrospinal fluid cytology will be assessed in Part 1 at screening, the EOT Visit, and in Part 2 at screening, end of Cycle 1 and Cycle 3, EOT Visit, and at each Follow-up Visit.

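### Appendix 6 sums different lesion sets for partial response and for progression within the brain, and does the reverse within the spine

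*Combined protocol and SAP*

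**What the plan says.** The response table in Appendix 6 has four cells with a size criterion that matter here.

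- Brain, PR: a fall of at least 50% from baseline "in the sum of the products of perpendicular diameters of all (up to 4) measurable lesions sustained for at least 4 weeks".
- Brain, PD: a rise of at least 25%, "compared with smallest measurement at any timepoint) in the sum of the products of perpendicular diameters of all measurable lesions", with no cap.
- Spine, PR: a fall of at least 50% from baseline "in the sum of the products of perpendicular diameters of all measurable lesions sustained for at least 4 weeks", with no cap.
- Spine, PD: a rise of at least 25%, "compared with smallest tumor measurement at any timepoint) in the sum of the products of perpendicular diameters of all (up to 4) measurable lesions".

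Section 7.3.2 gives the combination rule: "objective response and stable disease requires that all criteria are met, while progression is defined when any of the PD criteria are met". It also defines the endpoint: "ORR will be defined as the proportion of all evaluable patients achieving a CR or PR as best overall response at the time of assessment". Section 7.3.1 takes progression for PFS from the same table. Section 7.2.3 says which MRI sequence to measure on, but gives no number of lesions and no selection rule.

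Inclusion criterion 4 (Section 4.1) admits multifocal recurrent and leptomeningeal disease. Exclusion criterion 2 (Section 4.2) limits the size of a lesion to 15 mm in smallest diameter, not the number of lesions.

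**The concern.** PR is judged against a baseline sum and PD against the smallest sum. If the two sums cover different lesions, they are not the same measurement at two times, and the categories in one compartment no longer lie on one scale. Stable disease in the MRI rows is whatever remains after CR, PR and PD, so it inherits the mismatch.

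The companion clauses do not close the gap. The PR cells add a condition only on nonmeasurable disease (brain: "perpendicular diameters of all (up to 4) measurable lesions sustained for at least 4 weeks; no progression of nonmeasurable disease"; spine: "perpendicular diameters of all measurable lesions sustained for at least 4 weeks; no progression of nonmeasurable disease. If negative at baseline, must remain negative"). Besides the sum, the PD cells add nonmeasurable progression and new tumor. An existing fifth measurable lesion that grows is neither nonmeasurable nor new. It therefore falls outside the size criterion for brain PR and for spine PD.

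Response is assessed by the investigator on locally performed MRI in an open-label trial, so the choice of the four lesions is left to each site. ORR, DoR and PFS are all scored from these cells.

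**Working it through.** **The plan's own figure.** Section 8.1 assumes 20 evaluable patients and 5 responders, with a lower 95% limit of 9%. Section 8.4.1 names Clopper-Pearson. For x responders out of n, the lower limit is the 2.5% quantile of Beta(x, n − x + 1) and the upper limit is the 97.5% quantile of Beta(x + 1, n − x). For 5/20 this gives 8.66% to 49.10%, which reproduces the stated 9%.

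**Lesion arithmetic.** The documents give no lesion data, so these sets are assumed. Take six measurable lesions in one compartment with baseline products 100, 100, 100, 100, 80 and 80 mm². The first four sum to 400 and all six to 560. Assume that the smallest earlier sum equals baseline, that the first four are the ones chosen under the cap, and that any decrease is sustained for 4 weeks. Change = new sum / old sum − 1.

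| Case | First four (each) | Other two (each) | Change on four | Change on all six | Size criterion met |
|---|---|---|---|---|---|
| A | 45 | 80 | 180/400: −55% | 340/560: −39.3% | PR in brain, not in spine |
| B | 45 | 265 | 180/400: −55% | 710/560: +26.8% | PR and PD together in brain |
| C | 100 | 160 | 400/400: 0% | 720/560: +28.6% | PD in brain, not in spine |
| D | 130 | 80 | 520/400: +30% | 680/560: +21.4% | PD in spine, not in brain |
| E | 55 | 0 | 220/400: −45% | 220/560: −60.7% | PR in spine, not in brain |

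Two further assumed sets show the uncounted growth directly.

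- Brain, seven lesions: the four chosen go from 400 to 190 mm² (−52.5%), and the other three from 200 to 340 mm² (+70%). The full sum goes from 600 to 530 (−11.7%). The PR size cell is met and the PD size cell is not. On one all-lesion set this would be stable disease by size.
- Spine, eight lesions of 36 mm²: the four chosen stay at 4 × 36 = 144 (0%), and the other four double to 4 × 72 = 288. The full sum goes from 288 to 432 (+50%). The PD size cell is not met.

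With four or fewer measurable lesions in a compartment the two sets coincide and nothing changes.

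**Effect on ORR.** One patient in 20 is 1/20 = 5 percentage points.

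| Responders | ORR | 95% CI |
|---|---|---|
| 4/20 | 20% | 5.7% to 43.7% |
| 5/20 | 25% | 8.7% to 49.1% |
| 6/20 | 30% | 11.9% to 54.3% |

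The share of patients with more than four measurable lesions in one compartment is not given. The shift may be zero if there are none, and it is 5 points for each patient reclassified.

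**The case against.** **The cited criteria may settle it.** The table is labelled as adapted from published recommendations, to which Sections 7.2.3 and 7.3.2 also refer. The definition of a measurable lesion and the choice of targets may stand there. That source is not available here, so it cannot be said whether the asymmetry was inherited or introduced, or whether the source closes the gap. It also means that the eight small spinal lesions in the example might not all count as measurable; if they do not, the nonmeasurable-disease clauses apply instead. This limits what can be said about the effect. It does not remove the mismatch, because Appendix 6 is the table that the protocol prints for sites to apply.

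**Each cell is clear for its own category.** A reader might infer that ORR and PFS depend on which cell a site picks. They do not: each category has its own cell, and the all/any rule is stated. Where brain PR and PD size criteria are both met (case B), that rule points to PD, although no order of precedence is written. What stands is narrower: which lesions are summed.

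**Progression can be reached by other routes.** A reader might infer that growth of further spinal lesions can never become a PFS event. That is too strong. New tumor, significant nonmeasurable progression, newly positive cytology, clinical deterioration and new sites outside the CNS each suffice for PD, and death is a PFS event. Treatment can also be stopped on the investigator's or sponsor's judgment (Section 4.3.2.1).

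**Affected patients may be few.** A reader might infer that children with more than four measurable lesions are to be expected. The documents make them eligible and say nothing about how many. Focal disease, and radiographic remission with positive cytology, are eligible too.

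**The endpoints are secondary.** ORR, DoR and PFS are descriptive in Part 2, with confidence intervals and no success threshold. This stands.

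**Conclusion.** The point holds as an inconsistency in the scoring rule. Applied as printed, Appendix 6 scores PR and PD on different lesion sets within each compartment, in opposite directions for brain and spine, and Sections 7.2.3, 7.3.1 and 7.3.2 do not reconcile them. The same lesion changes can be PD by size in one compartment and not in the other, and the brain PR size criterion can be met while other measurable lesions grow.

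The reach is limited to patients with more than four measurable lesions in one compartment, and to ORR, DoR and PFS in Part 2. The primary endpoints and the sample-size figures are unaffected. The wording of the cells is certain. The effect on the results cannot be computed from the documents; the lesion examples are constructed to show direction, and the 5 points per patient would follow from any single reclassification among 20.

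**What to change.** Before any Part 2 response is scored, check the four cells against the cited criteria and amend Appendix 6 so that:

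- one lesion set per compartment, selected at baseline by a stated rule, is used for both PR (against baseline) and PD (against the smallest sum);
- if that set is capped at four, the text says how measurable lesions outside it count toward PR and toward PD, in terms that a site can apply.

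The documents do not settle whether the set should be capped; the need is that PR and PD agree and that the choice is made before the data are seen. Because disease progression is also a reason for ending treatment in Section 4.3.2.1, the sponsor should reconcile that section with the amended table. This point does not propose a treatment-stopping rule.

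The cost is the wording of Appendix 6 and the tumor-assessment page of the eCRF. No extra scans or readers are needed.

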## Appendix 7: Intracerebroventricular Access Device/CSF Flow Assessment

The following is an example of intracerebroventricular access device (e.g., Ommaya)/CSF flow assessment. Local assessment may be used in case this fulfills similar requirements.

CSF CISTERNOGRAM:	Evaluate CSF circulation
INDICATIONS:	Determine patency and flow from indwelling intracerebroventricular access device (e.g., Ommaya)
PATIENT PREPARATION:	None
Radio pharmaceutical:	Indium (In) 111 Diethylenetriamine Pentaacetic Acid (  In-DTPA)
Dose:	0.5 mCi for cisternal infusion via indwelling intracerebroventricular access device (e.g., Ommaya)
Instrument:	Dual-detector gamma camera
Isotope Energy Peak:	 In-DTPA: Medium Energy General Purpose (MEGP) 173, 247 keV
Energy Window Width:	20%

1. Only fresh, undiluted radiopharmaceutical from a newly opened vial should be used.
2. Patients infused in an indwelling intracerebroventricular access device (e.g., Ommaya) should have anterior, posterior, and lateral images of the head as well as anterior and posterior images of the spine and chest recorded immediately following infusion. Additional views should be recorded at 4, 6, and 24 hours as necessary.
3. The collimator should be placed as close as possible to the patient. Ten-minute acquisitions are obtained for each pair of views (anterior posterior and lateral views of the head, as well as anterior and posterior views of the spine are obtained at each time period).
4. Single-photon emission computed tomography (SPECT) images (optional) may be recorded in a 128 × 128 matrix for 30 seconds per stop, 3-degree steps, using a 360-degree acquisition. The detectors should be as close as possible to the head – preferably positioning the detectors above the shoulders.
5. Data are reviewed to determine the timing and of tracer entry and clearance from each of the cisterns and the region of the pacchionian granulations in region of the superior sagittal sinus.

Abnormal scan findings:

- a) Ventricular outflow obstruction - no egress beyond basal cisterns;
- b) Obstruction within spinal canal;
- c) Failure to ascend to the convexities by 6 hours (after infusion of the radiopharmaceutical), and spread over the convexities by 24 hours.

Only patients with sufficient flow should be dosed. Efforts to correct CSF flow can be installed and if sufficient flow is established, the patient should be dosed (see exclusion criterion # 1).

Signature Page for CLIN-000019 v8.0

